10.4.3 Study Blind

The sponsor, contract research organization (CRO), Investigator, staff at the study site, study monitors, and data analysis/management personnel will be blinded to the subject’s treatment

CONFIDENTIAL PROTOCOL

A Multi-Center, Double-Blind, Randomized, Vehicle-Controlled, Parallel-Group Study Comparing Tazarotene Cream 0.1% to TAZORAC® (tazarotene) Cream 0.1% and Both Active Treatments to a Vehicle Control in the Treatment of Acne Vulgaris

assignment. The subject will be requested not to discuss the appearance of the IP tube with the Investigator or study staff outside of the [REDACTED]. The tubes of Test, Reference and Placebo products will be blinded with identical outer cartons and labels. This will allow the study to be conducted under double-blind conditions (i.e., such that neither the subject nor the Investigator or study staff members will know the identity of the subject's treatment).

Each study site will have an [REDACTED]. The [REDACTED] is blinded to the treatment arm that each subject has been randomized to. [REDACTED]

To ensure that information that could potentially bias handling of data is not disclosed, access to the master randomization code will be extremely limited. A sponsor representative who is not involved in clinical development or the study conduct will provide initial approval of the final code to [REDACTED] upon code generation. A member of the sponsor Pharmacovigilance department will have access to the code in case of a safety emergency and in order to expedite FDA reporting, if applicable. Otherwise, the packaging company ([REDACTED]) will hold the master randomization code until after database lock. No parties (CRO, clinical sites or sponsor) involved in the conduct of the study will have access to the master randomization code until after database lock.

Breaking the blind must be considered only when knowledge of the treatment assignment is deemed essential by the Investigator for the subject's care. Whenever possible, if the Investigator feels that the subject should be unblinded, the Investigator should contact the [REDACTED] Medical Monitor to discuss the circumstances and come to an agreement before breaking the blind. If the [REDACTED] Medical Monitor cannot be reached, then the [REDACTED] or designee should be contacted before unblinding. [REDACTED] staff will notify the sponsor if they have received any requests to break the blind. This process will be documented, shared with the sponsor and filed.

CRO Contacts

[REDACTED]
Cell Phone: [REDACTED]

Phone: [REDACTED]

Fax: [REDACTED]

Email: [REDACTED]

Or:

[REDACTED]
Phone: [REDACTED]

CONFIDENTIAL PROTOCOL

A Multi-Center, Double-Blind, Randomized, Vehicle-Controlled, Parallel-Group Study Comparing Tazarotene Cream 0.1% to TAZORAC® (tazarotene) Cream 0.1% and Both Active Treatments to a Vehicle Control in the Treatment of Acne Vulgaris

Fax: [REDACTED]
Email: [REDACTED]

If a decision is made to unblind the subject, the Investigator will contact the [REDACTED] [REDACTED] telephone number for the subject's treatment assignment information and document the process in the subject's source documentation. The [REDACTED] unblinding telephone number is available 24 hours a day.

[REDACTED]
[REDACTED]

In the event the blind is broken for any reason, the Investigator will notify [REDACTED] as soon as possible, preferably within 24 hours, in writing with the details of the occurrence. [REDACTED] staff will notify the sponsor.

At the conclusion of the study, after the database has been locked, each site will be sent a sealed envelope containing the full study randomization scheme that should be retained with the study documents in the event of an FDA Inspection.

10.4.4 IP Shipment, Retention and Storage

The IPs will be shipped to each Investigator's site from [REDACTED], a centralized distribution center. Upon receipt of the IP, the Principal Investigator (or designee), must immediately inventory the material and confirm receipt with the sponsor, per the instructions included in the shipment. [REDACTED]

[REDACTED]

The Principal Investigator at each site will then ensure that all IP is stored in a locked, secure location, with access limited to the Investigator and his/her designee(s). [REDACTED] All IP will be stored at 20°C to 25°C (68°F to 77°F), with excursions permitted from -5°C to 30°C (23°F to 86°F). The temperature of the storage location must be monitored on a daily basis and any excursion beyond the required temperature storage range should be reported to the sponsor. An accurate inventory of the IP over the course of the study (i.e., dispensed and returned) will be maintained in accordance with federal regulations.

Initial supply quantities will be based on each site's projected enrollment quantities. Resupply will be conducted as needed based on remaining in-house supply and continued enrollment projections. Multiple full blocks of IP will be included in every shipment to the Investigator. [REDACTED]

[REDACTED]

CONFIDENTIAL PROTOCOL

A Multi-Center, Double-Blind, Randomized, Vehicle-Controlled, Parallel-Group Study Comparing Tazarotene Cream 0.1% to TAZORAC® (tazarotene) Cream 0.1% and Both Active Treatments to a Vehicle Control in the Treatment of Acne Vulgaris

number to the subject based upon a [REDACTED]. [REDACTED] will then assign the subject a [REDACTED] in a blinded fashion at Visit 1. This kit box number will correspond to a specific treatment group within [REDACTED]; however the treatment group will be unknown to the Investigator, the CRO, the sponsor and the subject. The site will record the randomization number and the kit box number in the subject's source documentation and drug dispensing log. The [REDACTED] will then dispense [REDACTED].

[REDACTED] At Visits 2, 3 and/or Unscheduled Visit, additional IP may be dispensed to the subject, as needed. [REDACTED]

[REDACTED] If an additional kit is required at either of these visits, the subject information will again be entered into [REDACTED]; however, [REDACTED] will now assign an additional kit containing tubes from the same treatment arm. The same process will be followed for the dispensing and recording of additional kit boxes and tubes. Each subject will maintain the same treatment assignment throughout the study.

10.4.6 Compliance

Subjects and/or their parent/caregiver will be provided with a diary to record the date of Day 1, the time and date of dosing, any missed doses, other concomitant medications and any AEs. Subjects taking fewer than [REDACTED] or more than [REDACTED] of the required doses over the 84 days \pm 4 days, or who missed scheduled applications for [REDACTED] consecutive days will be considered non-compliant with dosing, and excluded from the PP population. Compliance with dosing will be verified by the use of the subject diaries and discussion with the subject. Compliance criteria are as outlined in the table below:

Study Design			Compliance Criteria	
[REDACTED]	Treatment Duration	Scheduled Doses	[REDACTED]	[REDACTED]
[REDACTED]	84 Days	84	[REDACTED]	[REDACTED]

For subjects who are terminated from the study early, compliance will be determined from their duration in the study, up to the time they are considered early terminated. Subjects taking fewer than [REDACTED] of the required doses will be considered non-compliant with dosing. For example, if a subject is dropped from the study after [REDACTED] days of enrollment and doses [REDACTED] times, then percent compliance is [REDACTED].

10.5 Study Conduct

10.5.1 Visit 1 (Day -14 to Day 1): Screening and Baseline Evaluation

1. **Informed Consent/Assent:** Subjects who are willing to comply with study procedures will read, understand and sign the IRB-approved informed consent and/or assent, as appropriate. For a subject considered to be a minor in the state he/she is screened, the parent or legal

CONFIDENTIAL PROTOCOL

A Multi-Center, Double-Blind, Randomized, Vehicle-Controlled, Parallel-Group Study Comparing Tazarotene Cream 0.1% to TAZORAC® (tazarotene) Cream 0.1% and Both Active Treatments to a Vehicle Control in the Treatment of Acne Vulgaris

- guardian will be required to sign the ICF and the subject will sign an IRB-approved “assent to participate” form, as applicable.
2. **Medical History, Baseline Demographics and Concomitant Medications:** Review the subject’s demographics and medical history including concomitant medication use within the last 6 months.
 3. **Pregnancy Test:** A pregnancy test will be required of all female subjects of childbearing potential before randomization.
 4. **Vital Signs:** Blood pressure, pulse, temperature and respiration rate will be recorded for each subject.
 5. **Application Site Reactions:** A Medical Investigator (MD, DO, CRNP or PA) will grade the individual signs and symptoms. This will serve as a baseline for subsequent assessments of application site reactions. See Appendix B.
 6. **Investigator’s Global Assessment:** A Medical Investigator (MD, DO, CRNP or PA) will confirm the diagnosis of acne vulgaris and will perform a severity rating according to the IGA to determine the severity of the acne. See Appendix A.
 7. **Lesion Count:** A validated/qualified staff will perform the count of inflammatory lesions (i.e., papules and pustules), non-inflammatory lesions (i.e., open and closed comedones) and nodulocystic lesions (i.e., nodules and cysts).
 8. **Inclusion/Exclusion Criteria Review:** Confirm the subject meets all inclusion criteria and none of the exclusion criteria.
 9. **Randomization:** Eligible subjects selected for enrollment will be assigned a randomization number using [REDACTED].
 10. **Dispense IP, Supplies, Subject Instructions and Diary:** Randomized subjects will be allocated a specific kit of IP via [REDACTED]. The site will pull this specific kit for the subject and dispense [REDACTED]. The site will also dispense study supplies (i.e., cleanser and sunscreen) and a diary. The site will instruct the subject on the use of the IP, the completion of the diary and review the medications and/or treatments that are prohibited during the study.
 11. **First Dose with IP:** The site will instruct the subject on when the first dose of IP will be applied, which will be considered Day 1. The subject will record the date of Day 1 in their diary.

[REDACTED]

For all other subjects, the first dose (Day 1) of IP will be applied on the evening of Visit 1.

CONFIDENTIAL PROTOCOL

A Multi-Center, Double-Blind, Randomized, Vehicle-Controlled, Parallel-Group Study Comparing Tazarotene Cream 0.1% to TAZORAC® (tazarotene) Cream 0.1% and Both Active Treatments to a Vehicle Control in the Treatment of Acne Vulgaris

10.5.2 Visit 2 (Day 28 ± 4 days): Interim Visit

1. **Assess Health Status:** Review the subject's use of any new or ongoing concomitant medications and report any AEs.
2. **Pregnancy Test:** A urine pregnancy test will be required of all female subjects of childbearing potential.
3. **IGA:** A Medical Investigator will perform a severity rating according to the IGA to determine the severity of the acne. See Appendix A.
4. **Lesion Count:** A validated/qualified staff will perform count of inflammatory lesions (i.e., papules and pustules), non-inflammatory lesions (i.e., open and closed comedones) and nodulocystic lesions (i.e., nodules and cysts).
5. **Application Site Reactions:** A Medical Investigator will evaluate any Application Site Reactions since the last visit. See Appendix B.
6. **Collect and Review Subject's Diary:** Collect the diary from the subject and review for compliance with the protocol requirements. If the diary is not returned, the staff will collect available information based on discussion with the subject.
7. **IP Collection, Assessment and Dispensing (as needed):** Review the previously dispensed IP for usage. If a tube is empty, collect it from the subject. If a tube still contains significant product, re-dispense the tube to the subject. The subject should be dispensed enough IP to complete all required doses until Visit 3. [REDACTED]
[REDACTED] Record any lost or significantly damaged (i.e., punctured) IP.
8. **Dispense Supplies, Subject Instructions and Diary:** Dispense study supplies (i.e., cleanser and/or sunscreen), as needed, and a new diary with Subject Instruction sheet. Re-review proper use of the IP, the completion of the diary and the medications and/or treatments that are prohibited during the study.

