8.5 Risks and Benefits

The risks and benefits to subjects enrolled in clinical research studies that include a Placebo treatment group must be carefully considered based on three main criteria, namely: the disease being treated, the availability, efficacy and safety of approved therapies, and the scientific and statistical requirements of the desired outcome of the research study. The Office of Human Rights Protection (OHRP), a Division of the United States Federal Government's Department of Health and Human Services, has issued a detailed guidebook to Institutional Review Boards (IRBs) that includes discussion on the use of placebos in clinical studies.¹⁸

Randomized subjects will be enrolled in the study for 85 ± 4 days. Although the potential for any drug-related side effects of significance occurring during the study is low, the risk is higher in the two active treatment groups than in the Placebo group. Topical application of Tazarotene can lead to drug-related effects, mainly affecting the application sites: skin itching, irritation, dryness and burning or pain sensation represent the most common side effects.

CONFIDENTIAL PROTOCOL

A Multi-Center, Double-Blind, Randomized, Vehicle-Controlled, Parallel-Group Study Comparing Tazarotene Cream 0.1% to TAZORAC[®] (tazarotene) Cream 0.1% and Both Active Treatments to a Vehicle Control in the Treatment of Acne Vulgaris

All subjects enrolled in this study will receive Investigator evaluation of their condition over 85 days. In addition, the subject will be paid for their participation, and any payments will be reviewed by the investigational site's IRB and disclosed to the subject, via the informed consent form (ICF).

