10.6.7 IGA

At Visit 1, a Medical Investigator (MD, DO, CRNP or PA) should document a confirmed diagnosis of acne vulgaris.

At each visit, a Medical Investigator will perform an acne severity rating according to the IGA (see Appendix A). At Visit 1, the IGA must be a score 2, 3 or 4 for the subject to be eligible for inclusion. At Visit 4 (or Early Termination), the IGA score will be used to evaluate the secondary endpoint which is the proportion of subject considered a Clinical Success, with Clinical Success defined as an IGA score that is at least 2 grades less than the Baseline assessment.

The IGA is a static scale and no reference to previous scores for the subject should be made during this assessment.

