10.6.16 Health Status/AEs

At Visits 2, 3 and 4 subjects will be questioned regarding any changes in their medical status since their previous visit. Any significant health changes observed after signing of the ICF will be reported as AEs, as deemed appropriate by the Investigator.

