10.7.4 AE Documentation

Any AE (non-serious and serious) occurring after the subject has provided study-specific informed consent, and until the last study visit of the subject, has to be recorded on the AE pages of the eCRF.

The occurrence of AEs should be sought by non-directive questioning of the subject at each visit during the study. AEs also may be identified when they are volunteered by the subject during or between visits or during physical examination, laboratory test or other assessments. All AEs should be given appropriate medical care. Treatment may include one or more of the following: no action taken (i.e., further observation only); IP dosage adjusted/temporarily interrupted; IP permanently discontinued due to this AE; concomitant medication given; non-drug therapy given, subject hospitalized / subject's hospitalization prolonged. The treatment of the AE should be documented in the eCRF. In addition, the action taken with the IP should be documented, and should be assigned to one of the following categories: not changed, withdrawn, reduced, increased, interrupted, unknown and not applicable. Concomitant medication, other treatments or changes in the administration of the IP should be specified and documented.

Medical conditions/diseases present before starting IP are only considered AEs if they worsen after enrollment. Abnormal laboratory values or test results constitute AEs only if they induce clinical signs or symptoms, are considered clinically significant or require therapy.

Once an AE is identified, the Investigator should follow-up as specified below. Each time, the outcome should be documented and assigned to one of the following categories: not recovered/unchanged, condition deteriorating, recovered/resolved, improving/recovering, recovered/resolved with sequelae, fatal or unknown. The assessment of an AE should be made at each planned visit (or more frequently, if necessary). The Investigator should document in the eCRF any changes in seriousness, severity, the suspected relationship with the IP, the interventions required to treat it, and the outcome.

AEs occurring between informed consent and first dosing

Any AE occurring between study-specific informed consent and first dosing will be documented as "screening event", with an IP causality assessment "IP not yet administered".

CONFIDENTIAL PROTOCOL

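### At Visits 2–4 the AE and medication review is listed before the IGA and lesion count, and no readable rule shields the assessors from reported irritation

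*Protocol*

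**What the plan says.** In Protocol 10.5.2, 10.5.3 and 10.5.4, the step Assess Health Status comes first: "Review the subject's use of any new or ongoing concomitant medications and report any AEs". The IGA follows ("A Medical Investigator will perform a severity rating according to the IGA to determine the severity of the acne"), then the lesion count ("A validated/qualified staff will perform count of inflammatory lesions"), then reaction grading ("A Medical Investigator will evaluate any Application Site Reactions since the last visit"), then diary review.

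On how AEs are obtained, section 10.6.16 says: "At Visits 2, 3 and 4 subjects will be questioned regarding any changes in their medical status since their previous visit". Section 10.7.4 adds: "The occurrence of AEs should be sought by non-directive questioning of the subject at each visit during the study". Neither names the person who asks. Section 10.7 has site staff grade AE severity and the Investigator judge causality.

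Section 8.5 names itching, irritation, dryness and burning or pain as the most common side effects of tazarotene. Of drug-related side effects in general it says "the risk is higher in the two active treatment groups than in the Placebo group".

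Two readable safeguards bear on what an assessor may know. Section 10.4.3 asks subjects not to discuss how the tube looks. Section 10.6.7 says of the IGA that "no reference to previous scores for the subject should be made during this assessment".

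**The concern.** Both co-primary endpoints and the IGA are scored by an assessor at the site. A report of burning or itching heard shortly before scoring is a clue to treatment, because local irritation is the typical effect of the active drug and is expected less often on vehicle. If the clue reaches the assessor, scores may drift in favour of both actives.

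The comparisons at risk are those against Placebo. Section 8.4 includes Placebo to confirm the study's sensitivity and to guard against a false finding of equivalence, and both actives must beat it. A drift shared by the two actives would weaken that check. Visit 4 matters most because it supplies the Week 12 values. Early terminators follow the same Visit 4 procedures (section 10.3.5), and Visit 2 or 3 scores can enter the mITT superiority analysis through LOCF.

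**Working it through.** **1. Order of the steps.** The plan gives no figure to reproduce, so the main check is to set the lists side by side. Step numbers are from Protocol 10.5.2 to 10.5.4.

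| Step | Visit 2 | Visit 3 | Visit 4 |
|---|---|---|---|
| AE and medication review | 1 | 1 | 1 |
| Pregnancy test (if applicable) | 2 | 2 | 2 |
| Vital signs | – | – | 3 |
| IGA | 3 | 3 | 4 |
| Lesion count | 4 | 4 | 5 |
| Application site reactions | 5 | 5 | 6 |
| Diary review | 6 | 6 | 7 |

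The AE review precedes both efficacy assessments at all three visits. Reaction grading and diary review follow both.

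**2. What the first step can reveal.** The reaction scale (Appendix B) includes burning/stinging, itching and pain. These are felt by the subject, and an assessor cannot see them. Grading them is deferred until after scoring, but an open AE question at step 1 lets the same symptoms be volunteered earlier.

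**3. Who hears it.** A Medical Investigator rates the IGA and grades reactions. Validated staff count lesions (section 10.6.8). The AE interviewer is not named. Nothing in the readable text assigns the interview to an efficacy assessor, and nothing prevents it. The two safeguards cover tube appearance and previous IGA scores; neither covers symptoms.

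**4. Sensitivity of one superiority comparison (hypothetical).** The planning SDs are redacted, so SD is assumed to be 30, 40 or 50 percentage points. Group sizes are the enrolment targets, 444 active and 222 Placebo (section 11.2). The shift in favour of the active is also assumed and has no source in the documents.

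- SE = SD × √(1/444 + 1/222). For SD 40: 40 × 0.0822 = 3.29.
- Chance of a false result in favour of the active = 1 − Φ(1.96 − shift/SE). For SD 40 and a shift of 2: 1 − Φ(1.96 − 0.608) = 1 − Φ(1.352) = 8.8%.

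| Assumed shift (points) | SD 30 (SE 2.47) | SD 40 (SE 3.29) | SD 50 (SE 4.11) |
|---|---|---|---|
| 0 | 2.5% | 2.5% | 2.5% |
| 1 | 6.0% | 4.9% | 4.3% |
| 2 | 12.5% | 8.8% | 7.0% |
| 3 | 22.9% | 14.7% | 10.9% |

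**5. Test/Reference ratio (hypothetical).** The means are redacted too. Assume true reductions of 40 and 50, a ratio of 40/50 = 0.80. Adding 2 points to both gives 42/52 = 0.81; adding 5 gives 45/55 = 0.82; adding 10 gives 50/60 = 0.83. A proportional shift would leave the ratio unchanged.

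**The case against.** A reader might infer that the protocol has assessors told about retinoid irritation before they score. The documents do not support that. The AE interviewer is unnamed, the lesion counter may be a different person from the IGA rater, and AE questioning is non-directive. The numbered lists are not declared a binding sequence. The study schematic (Protocol 6.0, repeated in SAP section 3) puts lesion counts, IGA and application site reactions above adverse events. The structured questions on irritation already come after scoring.

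A reader might also take the table of error rates as the cost of the step order. It is not. The shift is assumed, and the table credits all of it to order, while visible erythema and dryness, reaction grading at earlier visits and the stated preference for the same lesion counter throughout would remain as cues after any reordering. The increment due to order could be near zero. The figures also concern one comparison, whereas section 11.6 requires both actives to succeed on both co-primaries, so false overall success is no more likely than its least likely component. The mITT groups will probably be smaller than the enrolment targets used here.

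All of this stands, and it limits the claim to a possibility of unknown size. It does not remove the gap. If the listed order is binding, it places AE information first. If it is not, the protocol has no readable rule on the matter.

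**Conclusion.** The point holds as an avoidable route to partial unblinding. The AE and medication review is listed ahead of both efficacy assessments at Visits 2 to 4, the protocol expects side effects more often on the actives, and no readable rule keeps reported symptoms from the assessors. The likely direction of bias favours both actives over Placebo.

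The size cannot be estimated from the documents, and the error rates above show only how one comparison would respond to an assumed shift. The conclusion rests on two assumptions: that the interviewer and the assessor overlap or share information at some sites, and that hearing of symptoms affects scoring. A reader might infer that equivalence is also materially threatened. Under the assumed means a 2-point additive shift moves the ratio only from 0.80 to 0.81, so the case rests on superiority.

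**What to change.** In Protocol 10.5.2, 10.5.3 and 10.5.4, move Assess Health Status to follow the IGA and lesion count. State that both must be recorded before the AE and concomitant-medication interview begins. Leave reaction grading and diary review after scoring, as now listed. This would also bring the visit lists into line with the schematic, where adverse events already stand below the efficacy assessments.

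The cost is an edit to the protocol and source worksheets with IRB review and approval (section 12.3.3), put into effect at about 25 sites. No added staff, visit or procedure is needed. The remedy is partial: it defers what subjects report at that visit, but visible erythema and dryness, and what assessors remember from earlier visits, stay as cues.
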